9.1. Screening Assessments

9.1.1. Medical and Surgical History

Medical history and cellulite history, including all prior procedures to treat cellulite, will be obtained at the Screening Visit. Medical history will include a review of the following systems: general, dermatological, respiratory, cardiovascular, gastrointestinal, genitourinary, gynecological, endocrine, musculoskeletal, hematological, neuropsychological, immune (allergies), and head, eyes, ears, nose, and throat. Historical and current medical conditions including date of last menstrual period will be recorded.

History of tobacco and alcohol use (never, current, former) will also be collected.

Medical and surgical history will include a review of all medical history and surgical procedures completed in the prior 10 years and any surgery completed at any time in the treatment area.

9.1.2. Physical Examination

A limited physical examination will be conducted at the Screening visit and will include evaluation of height and weight and the following organ systems: lungs, heart, abdomen, and extremities. Weight will also be recorded at the Days 1 and 180/ET visits.

All examinations will be performed by a qualified designated physician or health professional listed on the Form FDA 1572 and licensed to perform physical examinations. The investigator will review all physical exam findings for clinical significance. Any physical examination finding meeting the investigator's criteria for clinical significance will be recorded as an AE or SAE as appropriate.

9.1.3. Fitzpatrick Skin Scale

The Fitzpatrick Skin Scale is a 6-level scale (levels I-VI) for assessment of skin color and propensity for tanning. The skin types range from level I: Pale white skin, blue/hazel eyes, blond/red hair, always burns, does not tan to level VI: Dark brown or black skin, never burns, always tans darkly. The investigator (or qualified designated physician) will determine the Fitzpatrick skin type for all participants on Day 1. Only participants with a Fitzpatrick Skin level of I-IV will be included in the study.

9.1.4. Hexsel Cellulite Scale Severity

The Hexsel CSS is a photonumeric scale used to assess 5 key morphologic features of cellulite: (A) number of evident depressions, (B) depth of depressions, (C) morphological appearance of skin surface alterations, (D) laxity, flaccidity or sagging of skin, and (E) current classification scale based on medical literature (Hexsel et al, 2009; Nürnberger and Müller, 1978). Each of these features is evaluated on a 4-point scale from a low of 0 to a high of 3 (Table 4). Participants must have a Hexsel CSS total score \leq 12 to be included in the study. The Hexsel CSS Score will be assessed according to the time points on the Schedule of Assessments.

Table 4: Hexsel Cellulite Severity Scale

A – Number of Evident Depressions	0 = none/no depressions		
	1 = a small amount: 1-4 depressions are visible		
	2 = a moderate amount: 5-9 depressions		
	3 = a large amount: 10 or more depressions		
B – Depth of Depressions	0 = no depressions		
	1 = superficial depressions		
	2 = medium depth depressions		
	3 = deep depressions		
C – Morphological Appearance of Skin	0 = no raised areas		
Surface Alterations	1 = 'orange peel' appearance		
	2 = 'cottage cheese' appearance		
	3 = 'mattress' appearance		
D - Grade of laxity, flaccidity, or sagging	0 = absence of laxity, flaccidity, or sagging skin		
skin	1 = slight draped appearance		
	2 = moderate draped appearance		
	3 = severe draped appearance		
E – Current classification scale based on	0 = Grade or Stage $0 = $ There is no alteration of the skin surface.		
the scale originally described by Nürnberger and Müller (1978)	1 = Grade or Stage I = The skin of the affected area is smooth while the participant is standing or lying, but the alterations to the skin surface can be seen by pinching the skin or with muscle contraction.		
	2 = Grade or Stage II = The orange skin or mattress appearance is evident when standing, without the use of any manipulation (skin pinching or muscle contraction).		
	3 = Grade or Stage III = The alterations described in Grade or Stage II are present together with raised areas and nodules.		

9.1.5. Clinician Reported Photonumeric Cellulite Severity Scale

The Clinician Reported Photonumeric Cellulite Severity Scale (CR-PCSS)-Buttock will be used to assess the severity of cellulite of both treatment areas (each buttock, independently). The CR-PCSS-Buttock is a validated 5-level photonumeric scale developed specifically for investigators and used by the investigator to assess the severity of the participant's cellulite in each buttock by live assessments. The ratings range from 0 (None) to 4 (Severe) with labels and descriptors to aid the investigator in the assessments. This assessment should be made while the participant is in the standing position with relaxed gluteus muscles. Investigators who are physicians will be trained and qualified in the use of the CR-PCSS-prior to assessing any participants.

Participants must have a baseline CR-PCSS rating of '3' (moderate) or '4' (severe) on each buttock at the Screening Visit to be included in the study.

9.2. Efficacy Assessments

Efficacy assessments will be evaluated at times specified in the schedule of assessments. Below is a general description of each of these assessments. Specific instructions and questionnaires/forms (where appropriate) will be provided in the Study Operations Manual.

To ensure participant safety and protect data integrity, Endo, in accordance with the FDA Guidance on *Conduct of Clinical Trials of Medical Products During the COVID-19 Public Health Emergency* (March 2020, updated 30 August 2021), will allow remote visits for certain efficacy assessments. Additionally, participants impacted by the health emergency will be allowed to continue in the study and complete remaining assessments when the investigational sites re-open.

9.2.1. Digital Photography

At the time points indicated on the schedule of assessments, the investigator or qualified designee will photograph bilateral buttocks and each buttock individually while the participant is standing in a consistent, standard relaxed pose, with relaxed gluteus muscles using the supplied Canfield camera system.

Buttocks will be photographed at the following time points:

- Cohorts 1-6: Before and after marking the dimples and injection sites on Days 1, 22, and 43.
- Cohort 7: Before and after marking the dimples and injection sites on Days 1, 22, 43, and 64.
- During the treatment and follow-up visits designated in the Schedule of Assessments.
- For Cohort 4, photographs will be taken before and after marking the treatment areas. Photographs will include pre-marking images, and post-marking images delineating the perimeter of areas to be injected inclusive of injection site stencil.

All photographs taken by the investigator or qualified designee during this study are the property of Endo and de-identified images may be utilized for clinical development, scientific communication, corporate communication, marketing, regulatory purposes, and/or legal applications as required/desired by Endo.

Digital photographs captured by the investigator will be uploaded to a web-based repository using the Canfield camera system. Further information is provided in the Photography Manual in Study Operations Manual.

9.2.2. Investigator Assessment of Bruising Severity Scale

At the time points indicated on the Schedule of Assessments, the severity of bruising for each buttock will be documented on the Investigator Assessment of Bruising Severity Scale, a 5-point photonumeric scale with

- 0 =None or almost no bruising
- 1 = Mild bruising
- 2 = Moderate bruising

- 3 =Severe bruising
- 4 =Very severe bruising

The severity of bruising will be documented on the bruising page of the eCRF.

9.2.3. Investigator-Global Aesthetic Improvement Scale

At the time points indicated in the Schedule of Assessments, the investigator will determine the degree of improvement of each buttock by comparing treated cellulite dimples from the Day 1 pre-treatment (Baseline) digital image of each buttock to the treated dimples observed in a live assessment (Table 5). For each buttock, the investigator will provide the rating from those below that best represents his/her answer.

 Table 5:
 Investigator-Global Aesthetic Improvement Scale (I-GAIS)

Rating	Response Option	Description
+3	Very much improved	Optimal cosmetic result from treatment of the treated dimples
+2	Much improved	Marked improvement in the treated area appearance from before treatment, but not completely optimal
+1	Improved	Obvious improvement in the treated area appearance from before treatment, but additional treatment is indicated
0	No change	The treated area appearance is essentially the same as before treatment
-1	Worse	The treated area appearance is worse than before treatment
-2	Much worse	Marked worsening in appearance from the initial condition
-3	Very much worse	Obvious worsening in appearance from the initial condition

9.3. Safety Assessments

All safety assessments will be performed at the time points outlined in the Schedule of Assessments. Additional (unscheduled) safety assessments may be performed as needed.

To ensure participant safety and protect data integrity, Endo, in accordance with the FDA Guidance on *Conduct of Clinical Trials of Medical Products During the COVID-19 Public Health Emergency* (March 2020, updated 30 August 2021), will allow remote visits for certain safety assessments. Additionally, participants impacted by the health emergency will be allowed to continue in the study and complete remaining assessments when the investigational sites reopen.

9.3.1. Vital Signs

For Cohorts 1-7, vital signs (temperature, pulse, systolic blood pressure, and diastolic blood pressures) will be collected up to 2 hours prior to, and at 15 and 30 minutes after, QWO (CCH-aaes) administration on Days 1, 22, and 43. For Cohort 7, vital signs will also be collected on Day 64. Pulse and blood pressure will be collected after the participant has been sitting for 5 minutes. The investigator will review all vital sign values for clinical significance. Any vital sign value meeting the investigator's criteria for clinical significance will be recorded as an AE (or SAE, if appropriate).

9.3.2. Pregnancy Testing

All female participants of childbearing potential will have serum and/or urine pregnancy tests at the time points outlined in the Schedule of Assessments. Results must be available prior to QWO (CCH-aaes) administration. Participants with positive results at the Screening Visit or on Day 1 will be ineligible for study entry. Any female participant that becomes pregnant during the study will be immediately withdrawn from treatment and will have the pregnancy reported as per Section 9.4.5

For all female participant of childbearing potential, the participant's agreement to use contraception throughout their study participation (Screening Visit through the Day 180 Visit, or for a minimum of 28 days after the last dose of study intervention for participants who terminate early) will be documented.

9.3.3. Clinical Laboratory Determinations

At the time points listed in the Schedule of Assessments, clinical laboratory tests will be conducted. Required clinical laboratory tests are outlined in Section 11.2. Clinical laboratory tests will be performed by a designated central laboratory. Each site will be provided with instructions on specimen collection, preparation, packaging, and transport. The results of the tests will be returned to the investigational sites.

Samples for laboratory testing may be collected under fasted or nonfasted conditions. Fasting early morning samples are preferred, but a random daytime sample is acceptable. The date and time of the sample collection must be documented in the laboratory report. Investigators must review and sign laboratory reports and document the clinical significance of each laboratory abnormality. New clinically significant laboratory abnormalities or clinically significant changes in laboratory values will be reported as AEs (or SAEs, if appropriate).

Clinical laboratory test data will be reviewed by the investigator, or qualified designated physician, and additional clinical laboratory tests may be ordered at his/her discretion (eg, if the results of any clinical laboratory test falls outside the reference range or clinical symptoms necessitate additional testing to ensure safety). Any additional testing will be performed by the designated central laboratory if needed to ensure participant safety.

9.4. Adverse Events and Serious Adverse Events

The definitions of AEs and SAEs can be found in Section 11.3.

All AEs, including both observed or volunteered problems, complaints, signs or symptoms must be recorded, regardless of whether associated with the use of study intervention. Study intervention includes QWO (CCH-aaes) at the labeled dose and at different strengths (concentrations), diluent additives, depths of injection, and method of injection. This would include AEs resulting from concurrent illness, reactions to concurrent medication use, or progression of disease states (excluding the disease under study). A condition present at baseline that worsens after initiation of study intervention will be captured as an AE; the onset date will be the date the event worsened. The AE should be recorded in standard medical terminology when possible.

9.4.1. Time Period and Frequency for Collecting Adverse Event and Serious Adverse Event Information

SAEs and AEs will be collected by the investigator from the time of signing the informed consent through the Day 180 EOS/ET Visit.

Participants are encouraged to remain in the study for follow-up until the Day 180 Visit. Participants who discontinue from the study or study intervention and do not agree to remain in the study for follow-up until Day 180, will be asked to complete the 28-day post-treatment Safety Follow-up Visit (or phone call if a visit is not possible), if applicable. The status of any ongoing AEs/SAEs or the occurrence of any new AEs/SAEs will be determined.

Investigators are not obligated to actively seek AEs and SAEs after conclusion of study participation. However, if the investigator learns of any SAE, including death, at any time after the participant has been discharged from the study, and the investigator considers the event to be reasonably related to the study intervention or study participation, the investigator must notify the sponsor within 24 hours as described in Section 11.3.4.1.

All SAEs will be recorded and reported to the sponsor or designee within 24 hours. The investigator will submit any updated SAE data to the sponsor within 24 hours of it being available. The method of recording, evaluating, and assessing causality of AEs and SAEs and the procedures for completing and submitting SAE reports are provided in Section 11.3.

9.4.2. Method of Detecting Adverse Events and Serious Adverse Events

Care will be taken not to introduce bias when detecting AEs and SAEs. Open-ended and nonleading verbal questioning of the participant is the preferred method to inquire about AE occurrences.

At each visit, participants will be queried regarding any AEs that have occurred since the last visit. Study site personnel will then record all pertinent information. The study intervention compliance record should also be reviewed to detect potential intentional or unintentional overdoses.

In addition, investigators will document observed and elicited AE.

9.4.3. Follow-up of Adverse Events and Serious Adverse Events

After the initial AE/SAE report, the investigator is required to proactively follow each participant at subsequent visits/contacts. All ongoing AEs must be followed until they have resolved or for 28 days after the participant's last dose of study intervention, whichever comes first. All SAEs will be followed until they have resolved or the condition stabilizes, the event is otherwise explained, or until follow-up is no longer possible. Further information on follow-up procedures is provided in Section 11.3.

9.4.4. Regulatory Reporting Requirements for Serious Adverse Events

Prompt notification by the investigator to the sponsor of an SAE due to QWO (CCH-aaes) or other study interventions is essential so that legal obligations and ethical responsibilities regarding the safety of the study intervention under clinical investigation are met.

The sponsor has a legal responsibility to notify both the local regulatory authority and other regulatory agencies about the safety of the study intervention under clinical investigation. The sponsor will comply with country-specific regulatory requirements regarding safety reporting to regulatory authorities, Institutional Review Boards (IRBs), and investigators.

Investigator safety reports must be prepared for suspected, unexpected serious adverse reactions (SUSARs) according to local regulatory requirements and sponsor policy and forwarded to investigators as necessary. The Reference Safety Information for this study is the QWO Prescribing Information.

An investigator who receives a SUSAR IND Safety Report describing an SAE or other specific safety information (ie, summary or listing of SAEs) from the sponsor will review and then file it with their study documentation, and will notify the IRB, if appropriate according to local requirements.

9.4.5. Pregnancy

All pregnancies in participants identified during or after this study, where the estimated date of conception is determined to have occurred during the study or within 28 days of the last study intervention in participants who terminate from the study early, must be reported, followed to conclusion, and the outcome reported, even if the participant is discontinued from the study. The investigator should report (as outlined above) all pregnancies within 24 hours using the Pregnancy Form. Monitoring of the pregnancy should continue until conclusion and follow-up information detailing the progress and outcome must be submitted on 1 or more Pregnancy Form(s). A Two-Month Follow-up Pregnancy Form detailing the status of the infant should also be submitted.

Pregnancy itself is not regarded as an AE unless there is suspicion that the investigational product under study may have interfered with the effectiveness of a contraceptive medication. Likewise, elective abortions without complications are not considered AEs. Any SAEs associated with pregnancy (eg, congenital abnormalities/birth defects, or any other serious events) must additionally be reported as such using the Serious Adverse Event (SAE)/Reportable Event Form (see Section 11.3). Spontaneous miscarriages should also be reported and handled as SAEs.

Participants will be instructed to immediately notify the investigator of any pregnancies.

A participant who becomes pregnant must be withdrawn from the study. Should a participant discontinue treatment due to pregnancy, alternative treatment (if available) should be arranged according to standard of care, as determined by the investigator. Attempts to obtain the pregnancy follow-up and pregnancy outcome information detailed above are necessary even if a participant discontinues treatment because of pregnancy.

9.5. Treatment Overdose

Study intervention overdose is any accidental or intentional use of treatment in an amount higher than the dose indicated by the protocol for that participant. Study intervention compliance should be reviewed to detect potential instances of overdose (intentional or accidental).

Any treatment overdose during the study should be noted on the study intervention eCRF.

An overdose is not an AE per se, however all AEs associated with an overdose should both be entered on the AE eCRF and reported using the procedures detailed in Section 11.3, even if the events do not meet seriousness criteria. If the AE associated with an overdose does not meet seriousness criteria, it must still be reported using the Endo Serious Adverse Event (SAE)/Reportable Event Form and in an expedited manner but should be noted as nonserious on the form and the AE eCRF.

10. STATISTICAL CONSIDERATIONS AND METHODS

10.1. Sample Size Determination

The proposed sample size is approximately 210 participants. The sample size is based on evaluation of the different study interventions in 7 cohorts of up to 30 participants each, such that up to 168 participants complete the study.

10.2. Populations for Analysis

For the purposes of analysis, the following populations are defined:

The **Safety Population** is defined as all participants who received at least 1 injection of QWO (CCH-aaes). All safety analyses will be based on this population.

The **Full Analysis Set** is defined as all participants in the Safety Population who have at least 1 valid IABSS assessment at a treatment area after an injection of QWO (CCH-aaes). All efficacy analyses will be based on this population.

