While very rare, an allergic reaction to tranexamic acid may occur. To mitigate the risk of a hypersensitivity reaction, participants with a known hypersensitivity reaction to tranexamic acid will be excluded from study participation.

While relatively safe for use in most women, to mitigate the risk of thromboembolic events strict inclusion/exclusion criteria and addition of combination hormonal contraceptives and hormonal therapies as prohibited medications have been implemented within the study design to assist in mitigating the risk of thromboembolic events. Participants will be instructed to inform their physician should they have visual or ocular symptoms, or signs of an allergic reaction.

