session × 3 treatment sessions [Days 1, 22, and 43] for a maximum total dose of 5.04 mg). Participants in Cohort 6 will receive a maximum dose of up to 0.42 mg of QWO (CCH-aaes) on the control side and a maximum dose of up to 0.21 mg of QWO (CCH-aaes) on the investigational side per treatment session for 2 treatment sessions (Days 1 and 43) for a maximum total dose of 1.26 mg. All participants in Cohort 7 will receive a maximum dose of up to 0.84 mg of OWO (CCH-aaes) on the control side and a maximum dose of up to 0.84 mg of QWO (CCH-aaes) to the investigational side per treatment session × 3 treatment sessions for a maximum total dose of 5.04 mg. Participants in Cohort 7a will have the investigational side treated with QWO (CCH-aaes) on Days 1, 22, and 43 with the control side treated with QWO (CCH-aaes) on Days 22, 43 and 64. Treatment will be staggered for participants in Cohort 7b vs Cohort 7a. Participants in Cohort 7b will have the investigational side treated on Days 22, 43, and 64 and the control side treated on Days 1, 22, and 43. Tranexamic acid will be provided by the sponsor and self-administered by all participants enrolled in Cohort 7. Participants in Cohort 7a will take tranexamic acid 1300 mg orally TID for 5 days (prior to the day of the first injection of QWO (CCH-aaes) of the investigational buttock (Day -1), the day of the first injection (Day 1). and for the 3 days following the first injection (Days 2 to 4). Participants in Cohort 7b will take tranexamic acid orally TID for 5 days (prior to the day of the second injection on Day 21, the day of the second injection (Day 22) and for the 3 days following the second injection (Day 23 to Day 25).

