7. STUDY INTERVENTION

Study intervention comprises QWO (CCH-aaes) and different doses, different concentrations, and different methods of administration of QWO (CCH-aaes) including diluent additives designed to decrease bruising.

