10.3.2.1. Adverse Events

AEs will be coded using MedDRA by preferred term (PT) within each system organ class (SOC). All TEAEs will be summarized by cohort for each SOC and PT. A participant will only be counted once per SOC and PT. All summary tables will include number of occurrences of the TEAEs and the number and percent of participants that experienced the TEAEs.

In addition, for TEAEs of the injection site, the following variables will be summarized by cohort and treatment area for each SOC and PT: the number of occurrences of the TEAEs, the number and percent of participants that experienced the TEAEs, severity, and duration of the TEAEs.

Only TEAEs will be included in all summaries, and all AEs will be listed.

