11.3.1. Definitions

An AE is any unfavorable or unintended change in body structure (signs), body function (symptoms), laboratory result (eg, chemistry, ECG, X-ray, etc), or worsening of a preexisting condition associated temporally with the use of the study intervention whether or not considered related to the study intervention. Note: Any medical condition or laboratory abnormality already present at screening or baseline should be reported as medical history. If the medical condition present at baseline changes in severity or seriousness at any time during the study, it should be reported as an AE. AEs will be captured once a participant has signed the informed consent. AEs include:

- Changes in the general condition of the participant.
- Subjective symptoms offered by or elicited from the participant.
- Objective signs observed by the investigator or other study personnel.
- All concurrent diseases and/or medical occurrences that occur after the start of the study, including any change in severity or frequency of pre-existing disease.
- All clinically relevant laboratory abnormalities or physical findings that occur during the study.

A TEAE is any condition that was not present prior to treatment with study intervention but appeared following treatment, was present at treatment initiation but worsened during treatment, or was present at treatment initiation but resolved and then reappeared while the individual was on treatment (regardless of the intensity of the AE when the treatment was initiated).

An SAE is defined as an AE that:

- Results in death.
- Is immediately life-threatening (there is an immediate risk of death from the AE as it occurred; this does not include an AE that had it occurred in a more serious form may have caused death).
- Results in or prolongs an inpatient hospitalization (Note: a hospitalization for elective or preplanned surgery, procedure, or drug therapy does not constitute an SAE).
- Results in permanent or substantial disability (permanent or substantial disruption of one's ability to conduct normal life functions).
- Is a congenital anomaly/birth defect (in offspring of a participant using the study intervention regardless of time to diagnosis).
- Is considered an important medical event.

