5. ANALYSIS POPULATIONS

The study will use the following analysis populations for data summaries.

Table 16: Analysis Populations

Population Definition		Analysis	
Safety Population	The Safety Population is defined as all participants who received at least 1 injection of QWO (CCH-aaes).	All safety analyses will be based on this population	
Full Analysis Set (FAS)	The Full Analysis Set is defined as all participants in the Safety Population who have at least 1 valid IABSS assessment at a treatment area after an injection of QWO (CCH-aaes).	All efficacy analyses will be based on this population.	

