6.3.1. Imputation of Partial Dates

6.3.1.1. TEAE Status for Completely Unknown Start Date

The following rules will apply in cases where start date of an AE is completely unknown:

- If the AE onset date is unknown and the end date is on or after first injection on Day 1 or ongoing, then the AE will be considered a TEAE.
- If the AE onset date is unknown and the end date is before first injection on Day 1, then the AE will not be considered a TEAE
- If both the start and end dates are unknown (or end date is ongoing), then the AE will be considered a TEAE, following the worst-case principle.
- If the AE onset date is partly present and month/year is prior to the first injection date, then the AE will not be considered a TEAE.

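### Cohort 7a starts tranexamic acid the day before the first QWO injection, but the Safety Population, and on one reading the TEAE summaries, start only at that injection

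*Protocol*

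**What the plan says.** **Population.** Under protocol Section 10.2 the group analysed for safety "is defined as all participants who received at least 1 injection of QWO (CCH-aaes). All safety analyses will be based on this population". SAP Section 5 agrees: "The Safety Population is defined as all participants who received at least 1 injection of QWO (CCH-aaes". SAP Section 7.7 bases the safety summaries on that population.

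**Timing.** Protocol Section 5.1 puts the first tranexamic acid day in Cohort 7a "prior to the day of the first injection of QWO (CCH-aaes) of the investigational buttock (Day -1"). Section 7.4 has the tablets dispensed before the Day 1 visit. Eligibility is re-verified and the cohort assigned on Day 1. In Cohort 7b tranexamic acid starts on Day 21, after QWO has been injected into the control side on Day 1.

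**What counts as treatment-emergent.** The TEAE definition (protocol 11.3.1, SAP 4.6.1.1) is tied to treatment with study intervention. Protocol Section 7 reads: "Study intervention comprises QWO (CCH-aaes) and different doses, different concentrations, and different methods of administration of QWO (CCH-aaes) including diluent additives". Sections 9.4 and 11.3.2 likewise do not mention tranexamic acid, yet the titles of protocol Table 3 and SAP Table 8 call it a study intervention. For incomplete dates SAP 6.3.1.1 uses the injection: "If the AE onset date is unknown and the end date is before first injection on Day 1, then the AE will not be considered" treatment-emergent. A partial onset date whose month and year precede the first injection is handled the same way.

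**Reporting.** Protocol 10.3.2.1: "Only TEAEs will be included in all summaries, and all AEs will be listed". Protocol 11.3.1 also says: "Any medical condition or laboratory abnormality already present at screening or baseline should be reported as medical history". The same paragraph has AEs captured once consent is signed.

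**The concern.** These rules suit a trial in which QWO is the first product given. Cohort 7a breaks that order. The summary of changes for Amendment 02, which added Cohort 7, lists no change to Sections 9.4, 10.2 or 11.3, and SAP Table 18 does not take the matter up.

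The protocol describes this as the company's first study of oral tranexamic acid for QWO bruising. Among the risks it discusses are vascular occlusive events and hypersensitivity: "While very rare, an allergic reaction to tranexamic acid may occur". An early reaction is the kind of event that could fall on the first day of tablets and stop a participant from being injected. She is the one whom the population rule leaves out. The two 15-person sub-cohorts take the same course, and their safety results are comparable only if the same event is classified in the same way in both.

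**Working it through.** **1. Exposure before QWO.** Protocol Table 3 gives 2 tablets of 650 mg, three times a day, for 5 days: 2 × 3 × 5 = 30 tablets, which reproduces the 30-tablet bottle in Section 7.2.12. The course is 3 × 5 = 15 doses, or 30 × 650 = 19,500 mg.

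- Cohort 7a on Day -1: 3 of 15 doses = 6 of 30 tablets = 3,900 mg = 20%. If one Day 1 dose also precedes the injection, 4/15 = 26.7%.
- Cohort 7b before any QWO: 0 of 15 doses.

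**2. How the same reaction is classified.** Take a reaction on the first day of tranexamic acid, with a known onset date, that does not worsen later.

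| Case | Study intervention means QWO only | Tranexamic acid is a study intervention |
|---|---|---|
| 7a, injected on Day 1 | Not a TEAE; listed only | TEAE; summarised |
| 7a, never injected | Outside the Safety Population | Outside the Safety Population |
| 7b (onset Day 21) | TEAE; summarised | TEAE; summarised |

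The middle row does not depend on the reading. The top row does.

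**3. Incomplete dates.** Under SAP 6.3.1.1 an event of unknown onset that ends before the first injection is not a TEAE, whichever reading is taken. One that ends on or after the injection, or is ongoing, is a TEAE. The SAP 6.2 day formulas also disagree before Day 1: for an event one day earlier, AE Start Day is -1 + 1 = 0, while Study Day is -1.

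**4. Illustration: one Day -1 reaction among 15 women, with the SAP's Clopper-Pearson interval.**

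- Counted from the first dose of either product: 1/15 = 6.7% (95% CI 0.2% to 31.9%).
- Current text, injected, QWO-only reading: 0/15 = 0% (0% to 21.8%).
- Current text, not injected: 0/14 = 0% (0% to 23.2%).

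**5. How likely such an event is.** The documents give no Day -1 reaction rate. For assumed per-participant rates p, the chance of at least one in 15 is 1 - (1 - p)^15: 14% at p = 1%, 54% at 5%, 79% at 10% and 96% at 20%. For venous thromboembolism the protocol's own figure is one extra case per 78,549 women per 5-day course. For 15 women that is 15/78,549 = 0.019% over the whole course.

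**The case against.** A reader might infer that safety reporting as a whole begins at the first injection and that Day -1 events are lost. The documents do not support that. AEs and SAEs are collected from consent (protocol 9.4.1), SAEs go to the sponsor within 24 hours, all AEs are listed, AEs of screen failures are recorded (protocol 6.4), and participants excluded from the Safety Population are listed (SAP 7.1). What is lost is tabulation. The gap remains because rates are read from the summaries.

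A reader might also take it as settled that a Day -1 reaction is not a TEAE. It is not settled. For a known onset date the definition refers to study intervention, not injection, and two table titles give that label to tranexamic acid. The SAP 6.2 entry naming the first injection defines relative Day 1, not TEAE status. The fair statement is that the documents conflict.

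The medical-history route is weaker still. In Cohort 7a medical history is scheduled only at Screening, which is also where the schedule places dispensing, so a drug reaction would follow dispensing. The two sentences in 11.3.1 nevertheless point in different directions for an event that starts after consent and is present at baseline.

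Nor can one say that Cohort 7a rates will be understated. That needs an event that does not worsen, or one that stops the injection. The 0/14 figure further assumes that the woman is one of the 15 and is not replaced, although assignment takes place on Day 1 and the no-replacement rules apply only after a first QWO dose.

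**Conclusion.** The point stands in a limited form, for Cohort 7a only. The exclusion of a woman who took tranexamic acid but was never injected follows directly from both documents. The TEAE status of a Day -1 event with a known date is ambiguous. For incomplete dates the SAP cut-off is the injection. As a result, the same reaction can be classified differently in 7a and 7b.

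All 15 planned Cohort 7a participants are affected for 20% of their planned doses, assuming that the course is taken as scheduled. The effect on reported rates cannot be stated; the one-event figures are hypothetical. The primary bruising endpoint is untouched. The correction is still worth making before database lock, because it is cheap and concerns a product whose safety alongside QWO this study is the sponsor's first chance to describe.

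**What to change.** - **Population (protocol 10.2, SAP 5).** Include everyone with at least one QWO injection or at least one dose of study tranexamic acid. Anyone who took tablets before the Day 1 cohort assignment is shown under intended Cohort 7a.
- **Definition (protocol 7, 9.4 and 11.3.2; SAP 3.15).** Name tranexamic acid as a study intervention.
- **TEAE onset (protocol 11.3.1; SAP 4.6.1.1 and 6.3.1.1).** Count from the first dose of either product. Align the AE Start Day formula with Study Day for onsets before Day 1.
- **Medical history (protocol 11.3.1, SAP 3.15.1).** Limit it to conditions present before that first dose.
- **Baselines (SAP 6.2, 7.7.4).** Keep the Day 1 pre-injection baselines for IABSS and vital signs. SAP 6.2 must say so explicitly: its baseline refers to the first dose of study intervention, so naming tranexamic acid would otherwise move it. IABSS is first scored on Day 1, so Cohort 7a would then have no IABSS baseline.

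The efficacy population does not change, because the Full Analysis Set also requires an IABSS score after a QWO injection. Cohorts 1 to 6 are unaffected. Tranexamic acid use already has its own eCRF page, so the cost is wording and a little programming. The downside is that the Cohort 7a safety denominator may include women who never received QWO; a footnote should give their number.
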